	Grade 3	Temporary dose interruption until recovery to Grade ≤1. Initiate appropriate medical therapy and monitor. Consider re-initiating Afinitor® at a lower dose. If toxicity recurs at Grade 3, consider discontinuation.
	Grade 4	Discontinue Afinitor® and treat with appropriate medical therapy.
Metabolic events (e.g. hyperglycemia, dyslipidemia)	Grade 1	No dose adjustment required. Initiate appropriate medical therapy and monitor.
	Grade 2	No dose adjustment required. Manage with appropriate medical therapy and monitor.
	Grade 3	Temporary dose interruption. Re-initiate Afinitor® at a lower dose. Manage with appropriate medical therapy and monitor.
	Grade 4	Discontinue Afinitor® and treat with appropriate medical therapy.

¹ Severity Grade description: 1 = mild symptoms; 2 = moderate symptoms; 3 = severe symptoms; 4 = life-threatening symptoms.

² If dose reduction is required, the suggested dose is approximately 50% lower than the dose previously administered.

³ Activities of daily living (ADL)

⁴ Avoid using agents containing alcohol, hydrogen peroxide, iodine, and thyme derivatives in management of stomatitis as they may worsen mouth ulcers.

Table 6-4 Dosing guidelines for study drug-related hematologic toxicities

Adverse event	Severity¹	Afinitor® Dose Adjustment
Thrombocytopenia (Platelet count	Grade 1 (<LLN-75.0x10 ⁹ /L)	No dose adjustment required.

Adverse event	Severity ¹	Afinitor® Dose Adjustment
decreased)	Grade 2 (<75.0-50.0x10 ⁹ /L)	Temporary dose interruption until recovery to Grade ≤1. Re-initiate Afinitor® at the same dose.
	Grade 3 (<50.0-25.0x10 ⁹ /L)	Temporary dose interruption until recovery to Grade ≤1. Re-initiate Afinitor® at a lower dose.
	Grade 4 (<25.0x10 ⁹ /L)	Temporary dose interruption until recovery to Grade ≤1. Re-initiate Afinitor® at a lower dose.
Neutropenia (Neutrophil count decreased)	Grade 1 (<LLN-1.5x10 ⁹ /L)	No dose adjustment required.
	Grade 2 (<1.5-1.0x10 ⁹ /L)	No dose adjustment required.
	Grade 3 (<1.0-0.5x10 ⁹ /L)	Temporary dose interruption until recovery to Grade ≤2 (ANC≥1.0x10 ⁹ /l). Re-initiate Afinitor® at the same dose.
	Grade 4 (<0.5x10 ⁹ /L)	Temporary dose interruption until recovery to Grade ≤2 (ANC≥1.0x10 ⁹ /l). Re-initiate Afinitor® at a lower dose.

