Febrile neutropenia	Grade 3 (ANC<1.0x10 ⁹ /L with single temperature >38.3°C (101°F) or sustained temperature ≥38°C (100.4°F) for >1h)	Temporary dose interruption until recovery to Grade ≤2 (ANC≥1.25x10 ⁹ /l) and no fever. Re-initiate Afinitor® at a lower dose.
	Grade 4 (Life-threatening consequences; urgent intervention indicated)	Discontinue Afinitor®.
Any hematologic toxicity requiring study drug interruption for >28 days		Discontinue Afinitor®.

¹ Grading based on National Cancer Institute (NCI) Common Terminology Criteria for Adverse Events (CTCAE) v4.03

All dose changes must be recorded on the Dosage Administration Record CRF.

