7.1.4 Discontinuation of study treatment

Patients may voluntarily discontinue from the study treatment for any reason at any time. If a patient decides to discontinue from the study treatment, the investigator should make a reasonable effort (e.g. telephone, e-mail, letter) to understand the primary reason for this decision and record this information in the patient's chart and on the appropriate CRF pages. They may be considered withdrawn if they state an intention to withdraw, fail to return for visits, or become lost to follow-up for any other reason.

The investigator may discontinue study treatment for a given patient if, he/she believes that continuation would be detrimental to the patient's well-being.

In addition to mandatory discontinuation reasons for study treatment listed in [Section 6.2](#), study treatment **must** also be discontinued under the following circumstances:

- Pregnancy
- Death
- Subject/Guardian decision
- Adjustments to study treatment due to toxicity that result in treatment discontinuation (see [Section 6.2](#))
- Any other protocol deviation that results in a significant risk to the patient's safety.

Patients who discontinue study treatment should NOT be considered withdrawn from the study. They should return for the assessments indicated in [Section 7.2.1](#). If they fail to return for these assessments for unknown reasons, every effort (e.g. telephone, email, letter) should be made to contact them as specified in [Section 7.1.7](#).

For patients who discontinue treatment for reasons other than documented disease progression, death, lost to follow-up, or withdrawal of consent, kidney lesion assessments must continue to be performed as per the schedule of assessments until documented disease progression (per independent radiology review), death, lost to follow-up, or withdrawal of consent.

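### In Protocol Table 6-4, the Grade 3 febrile neutropenia row equates Grade ≤2 with ANC ≥1.25 ×10⁹/L, although the same table starts Grade 2 at 1.0

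*Protocol*

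**What the plan says.** All the figures are in Protocol Section 6.2.2, Table 6-4. The quotes stop just before the exponent; the unit throughout is 10⁹/L.

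- **Neutrophil grades.** The neutropenia rows give "Grade 2 (<1.5-1.0x10" and "Grade 3 (<1.0-0.5x10".
- **Recovery after Grade 3 or Grade 4 neutropenia.** Both rows read "Temporary dose interruption until recovery to Grade ≤2 (ANC≥1.0x10".
- **Entry to Grade 3 febrile neutropenia.** The count condition is "Grade 3 (ANC<1.0x10", together with a temperature criterion.
- **Recovery after Grade 3 febrile neutropenia.** The row reads "Temporary dose interruption until recovery to Grade ≤2 (ANC≥1.25x10" and adds that fever must be absent. Treatment then resumes at a lower dose. Only Grades 3 and 4 are listed for this event, and Grade 4 leads to discontinuation.
- **Last row.** "Any hematologic toxicity requiring study drug interruption for >28 days" leads to discontinuation.
- **Grading scale.** One footnote covers the table: "Grading based on National Cancer Institute (NCI) Common Terminology Criteria for Adverse Events (CTCAE) v4.03".

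Two other statements bear on the table's force. The text of Section 6.2.2 presents Tables 6-3 and 6-4 as recommendations and leaves room for the treating physician's judgment. Section 7.1.4, in contrast, begins its list of stopping reasons with "In addition to mandatory discontinuation reasons for study treatment listed in" Section 6.2.

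**The concern.** The parenthesis after Grade ≤2 reads as the count equivalent of that grade. In the neutropenia rows it is: 1.0 is the lower limit of Grade 2. In the febrile neutropenia row the same label carries 1.25, which is not a grade boundary anywhere in the table. Nothing else in the Protocol or SAP explains that figure.

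A site with an afebrile patient at, say, ANC 1.1 after Grade 3 febrile neutropenia is told both that the required grade has been reached and that the required count has not. One reading ends the interruption; the other continues it. The last row of the table depends on the length of the interruption, so the choice of reading can also decide whether that row applies. Protocol Section 12 does not allow departures to be approved in advance, so the site cannot tell from the text which action complies.

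**Working it through.** No plan figure depends on a model here. The check compares each stated count with the table's own grade bands.

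**Step 1: translate the label.** Grade 2 runs from 1.0 to below 1.5, and Grade 3 from 0.5 to below 1.0. Grade ≤2 therefore means ANC ≥1.0.

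**Step 2: compare each row with that result.**

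| Row | Label | Count stated | Count implied by the table's bands | Agrees? |
|---|---|---|---|---|
| Neutropenia Grade 3 | Grade ≤2 | ≥1.0 | ≥1.0 | yes |
| Neutropenia Grade 4 | Grade ≤2 | ≥1.0 | ≥1.0 | yes |
| Febrile neutropenia Grade 3 | Grade ≤2 | ≥1.25 | ≥1.0 | no |

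The single footnote rules out a second grading scale. The febrile neutropenia entry has no Grade 1 or 2 of its own, so the label can refer only to the neutrophil grade.

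**Step 3: find the affected range.** For a patient whose fever has resolved after Grade 3 febrile neutropenia:

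| ANC (×10⁹/L) | Grade ≤2 met? | Count ≥1.25 met? | Result |
|---|---|---|---|
| below 1.0 | no | no | interruption continues on both readings |
| 1.0 to below 1.25 | yes | no | readings conflict |
| 1.25 or above | yes | yes | interruption ends on both readings |

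The conflict range is 1.25 − 1.0 = 0.25 wide. The Grade 2 band is 1.5 − 1.0 = 0.5 wide, so the range is 0.25 / 0.5 = 50% of it, the lower half. This is a width, not a probability that a patient falls there.

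**Step 4: apply the 28-day row.** The interruption begins at Grade 3 febrile neutropenia on either reading, so its start is not in doubt. Suppose the patient is afebrile, the ANC reaches 1.0 by day 28 and stays below 1.25 beyond day 28. On the grade reading the required interruption ended by day 28 and the row does not apply. On the count reading it runs past day 28 and the row applies. If the ANC is still below 1.0 after day 28, or reaches 1.25 without fever by day 28, both readings agree about this row.

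**Step 5: trace the effect on the analysis.** Laboratory grades are assigned by program from observed values (Protocol Section 10.4.3, SAP Section 5.3), so 1.25 does not enter them. Dose interruptions are derived from recorded doses (SAP Section 2.4.1). The tables of adverse events leading to discontinuation, or to dose adjustment or interruption (SAP Section 2.8.1), could differ only through what was actually done for an affected patient.

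**The case against.** **The stricter count may be intended.** A higher count after fever is a possible choice, and Protocol Sections 2.3 and 6.2.1 tie the dose and starting dose to product information that is not among these documents. The cell can also be followed as printed, because any ANC of 1.25 or more is also Grade ≤2, so a site that waits for the count satisfies both statements. This weakens any claim that the two readings are equally natural. It does not make the cell consistent, since the row gives 1.25 as the meaning of Grade ≤2, not as an added condition.

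**The table is guidance.** Section 6.2.2 supports this, and it limits the weight of the point. Section 7.1.4 pulls the other way for discontinuation reasons, so the objection stands only in part.

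**Broader readings the documents do not support.**

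- A reader might infer that the neutropenia and febrile neutropenia rows contradict each other because their counts differ. Different thresholds for different events are not in themselves a contradiction, and the neutropenia rows are consistent at 1.0. The fault lies inside one cell.
- A reader might note that one changed discontinuation among 40 patients is 1/40 = 2.5 percentage points. That is true of any single-patient event and says nothing about how likely this one is.
- A reader might see a threat to the primary endpoints, the incidence of adverse events and of laboratory abnormalities. Step 5 shows that the 1.25 figure does not enter their derivation.

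**It is late to change the cell.** According to the Amendment 2 rationale, all 40 patients had been enrolled and were on treatment. SAP Section 2.7.1 describes findings at database lock. This stands: a wording change would do little for these patients' care, and what remains useful is clarification and a look back.

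**Conclusion.** The inconsistency is real and can be shown from one table. It is minor. It affects only patients with study drug-related Grade 3 febrile neutropenia whose fever has resolved and whose ANC is from 1.0 to below 1.25 ×10⁹/L. For them the end of the interruption is unclear. The 28-day row comes into question only if that state is reached by day 28 and the ANC stays in the range beyond it.

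That the event is rare is an assumption: the documents give no expected frequency. Neutropenia is not among the common adverse events that Protocol Section 1.2.3 reports from the two earlier studies in this disease, which fits with few or no cases but does not establish it. Sample size, analysis sets and planned statistics are unaffected. The conclusion rests on reading the parenthesis as a gloss on the grade, as it plainly is in the neutropenia rows. It implies no view on which threshold is right.

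**What to change.** The sponsor's medical team should reconcile the grade label and the ANC figure in the Grade 3 febrile neutropenia cell of Table 6-4, and state which criterion ends the interruption for the 28-day row. Whether the label or the figure changes is their decision.

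Given the stage of the trial, the sponsor should also check the adverse event, laboratory and dosing records for any patient with Grade 3 febrile neutropenia and an afebrile ANC from 1.0 to below 1.25 during an interruption. The study report should state the result, including if there were none, and which criterion was applied to any such patient.

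The cost is one table cell, by clarification or amendment, and a search of data already collected. No visit, assessment or analysis needs to change.

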6.2.3 Management of specific toxicities

6.2.3.1 Management of infections

Everolimus has immunosuppressive properties and may predispose patients to bacterial, fungal, viral or protozoal infections, including infections with opportunistic pathogens. Localized and systemic infections, including pneumonia, other bacterial infections, invasive fungal infections, such as aspergillosis, candidiasis or pneumocystis jirovecii pneumonia (PJP) and viral infections including reactivation of hepatitis B virus, have been described in patients taking everolimus. Some of these infections have been severe (e.g. leading to sepsis, including septic shock, respiratory or hepatic failure) and occasionally have had a fatal outcome.

Physicians and patients should be aware of the increased risk of infection with everolimus. Treat pre-existing infections prior to starting treatment with everolimus. While taking everolimus, be vigilant for symptoms and signs of infection; if a diagnosis of infection is made, institute appropriate treatment promptly and consider interruption or discontinuation of everolimus.

If a diagnosis of invasive systemic fungal infection is made, discontinue everolimus and treat with appropriate antifungal therapy.

Cases of PJP, some with fatal outcome, have been reported in patients who received everolimus. PJP may be associated with concomitant use of corticosteroids or other immunosuppressive agents. Prophylaxis for PJP should be considered when concomitant use of corticosteroids or other immunosuppressive agents is required.

6.2.3.2 Management of stomatitis / oral mucositis / mouth ulcers

Patients with a clinical history of stomatitis/oral mucositis/mouth ulcers and those with gastrointestinal morbidity associated with mouth/dental infections, irritation of esophageal mucosa e.g. gastroesophageal reflux disease (GERD) and pre-existing stomatitis/mucositis must be monitored even more closely. Patients should be instructed to report the first onset of buccal mucosa irritation/reddening to their study physician immediately.

Stomatitis/oral mucositis/mouth ulcers due to study drug should be treated using local supportive care. Please note that investigators in earlier studies have described the oral toxicities associated with everolimus as mouth ulcers, rather than mucositis or stomatitis. If the clinical examination reveals mouth ulcers rather than a more general inflammation of the mouth, please classify the adverse event as such. Please refer to [Table 6-3](#) for management of stomatitis/oral mucositis/mouth ulcers.

In addition agents containing alcohol, hydrogen peroxide, iodine, and thyme derivatives may tend to worsen mouth ulcers. It is recommended to avoid these agents.

Antifungal agents should be avoided unless a fungal infection is diagnosed. In particular, systemic imidazole antifungal agents (ketoconazole, fluconazole, itraconazole, etc.) should be avoided in all patients due to their strong inhibition of everolimus metabolism, therefore leading to higher everolimus exposure. Therefore, topical antifungal agents are preferred if a fungal infection is diagnosed.

6.2.3.3 Management of hyperlipidemia and hyperglycemia

Treatment of hyperlipidemia should take into account the pre-treatment status and dietary habits of the patient. Grade 2 or higher hypercholesterolemia (>300 mg/dL or 7.75 mmol/L) or grade 2 hypertriglyceridemia or higher (>2.5x upper normal limit) should be treated with a 3-hydroxy-3-methyl-glutaryl (HMG)-CoA reductase inhibitor (e.g. atorvastatin, pravastatin, fluvastatin) or appropriate triglyceride-lowering medication, in addition to diet.

Note: Concomitant therapy with fibrates and an HMG-CoA reductase inhibitor is associated with an increased risk of a rare but serious skeletal muscle toxicity manifested by rhabdomyolysis, markedly elevated creatine phosphokinase (CPK) levels and myoglobinuria, acute renal failure and sometimes death. The risk versus benefit of using this therapy should

be determined for individual patients based on their risk of cardiovascular complications of hyperlipidemia.

Hyperglycemia has been reported in patients taking everolimus. Monitoring of fasting serum glucose is recommended prior to the start of study drug and periodically thereafter. More frequent monitoring is recommended when everolimus is co-administered with other drugs that may induce hyperglycemia.

6.2.3.4 Management of renal failure events

Cases of renal failure (including acute renal failure), some with a fatal outcome, have been observed in patients treated with everolimus. Renal function of patients should be monitored particularly where patients have additional risk factors that may further impair renal function. Monitoring of renal function, including measurement of blood urea nitrogen (BUN), urinary protein, and serum creatinine, is recommended prior to the start of study drug and periodically thereafter.

6.2.3.5 Management of non-infectious pneumonitis

Non-infectious pneumonitis is a class effect of rapamycin derivatives. Cases of non-infectious pneumonitis (including interstitial lung disease) have also been described in patients taking everolimus. Some of these have been severe and on rare occasions, a fatal outcome was observed.

A diagnosis of non-infectious pneumonitis should be considered in patients presenting with non-specific respiratory signs and symptoms such as hypoxia, pleural effusion, cough or dyspnea, and in whom infectious, neoplastic and other non-medicinal causes have been excluded by means of appropriate investigations. Opportunistic infections such as PJP should be ruled out in the differential diagnosis of non-infectious pneumonitis. Patients should be advised to report promptly any new or worsening respiratory symptoms.

Patients who develop radiological changes suggestive of non-infectious pneumonitis and have few or no symptoms may continue everolimus therapy without dose alteration.

If symptoms are moderate (grade 2), consideration should be given to interruption of therapy until symptoms improve. The use of corticosteroids may be indicated. Everolimus may be reintroduced at a daily dose approximately 50% lower than the dose previously administered.

For cases of grade 3 non-infectious pneumonitis, interrupt everolimus until resolution to less than or equal to grade 1. Everolimus may be re-initiated at a daily dose approximately 50% lower than the dose previously administered depending on the individual clinical circumstances. If toxicity recurs at grade 3, consider discontinuation of everolimus. For cases of grade 4 noninfectious pneumonitis, everolimus therapy should be discontinued. Corticosteroids may be indicated until clinical symptoms resolve.

For patients who require use of corticosteroids for treatment of non-infectious pneumonitis, prophylaxis for PJP may be considered.

Individuals participating in this study will be routinely questioned as to the presence of new or changed pulmonary symptoms consistent with lung toxicity. Moreover, potential lung radiological changes can be detected by the chest CT/MRI scans that are performed on all

patients with LAM for tumor assessment according to the schedule of events ([Table 7-1](#)). In addition, pulmonary function tests (PFTs), including spirometry, DLCO, and room air O₂ saturation at rest should be performed. Bronchoscopy with biopsy and/or bronchoalveolar lavage (BAL), should be conducted, if clinically indicated, to monitor for pneumonitis. If non-infectious pneumonitis develops, the guidelines in [Table 6-3](#) should be followed. Consultation with a pulmonologist is recommended for any case of pneumonitis that develops during the study.

6.3 Concomitant medications

Concomitant medications and therapies for adverse events or supportive treatments are permitted. Some medications may however have drug-drug interactions with everolimus and the guidelines below should be followed.

In clinical studies and post-marketing spontaneous reports, angioedema has been reported with and without concomitant use of angiotensin-converting-enzyme (ACE) inhibitors. The risk of angioedema events may be increased with concomitant administration of ACE inhibitors.

Cytochrome P450 and P-glycoprotein (PgP) inhibitors/inducers/substrates

Everolimus is metabolized by CYP3A4 in the liver and to some extent in the intestinal wall.

Therefore, the following are recommended:

- Co-administration with strong inhibitors of CYP3A4/PgP should be avoided and may cause increased everolimus concentrations.
- Co-administration with moderate CYP3A4/PgP inhibitors should be used with caution. If a patient requires co-administration of moderate CYP3A4/PgP inhibitors, reduce the dose of study drug to half the currently used dose. Additional dose reductions may be required to manage toxicities. If the inhibitor is discontinued, consider a washout period of at least 2-3 days (average for the most commonly used moderate inhibitors), before the study drug dose is returned to the dose used prior to initiation of the moderate CYP3A4/PgP inhibitor.
- Co-administration with strong inducers of CYP3A4 should be avoided.
- If a patient requires co-administration of strong CYP3A4 inducer, an increase in the dose of study drug up to twice the currently used daily dose should be considered, using 5 mg increments or less. This dose adjustment of study drug is predicted to achieve similar AUC to the range observed without inducers. However, there are no clinical data with this dose adjustment in patients receiving strong CYP3A4 inducers. If the strong inducer is discontinued, consider a washout period of at least 3-5 days (reasonable time for significant enzyme de-induction), before the study drug dose is returned to the dose used prior to initiation of the strong CYP3A4/PgP inducer.

Please refer to [Table 6-5](#) listing relevant inducers and inhibitors of CYP3A and to [Table 6-6](#) for a list of relevant substrates, inducers, and inhibitors of PgP.

Table 6-5 Clinically relevant drug interactions: inducers, and inhibitors of isoenzyme CYP3A4

Inducers

Strong inducers:

avasimibe, carbamazepine, phenytoin, rifampin, St. John's wort (HYPERICUM PERFORATUM), rifabutin, phenobarbital, mitotane, enzalutamide

Moderate inducers:

bosentan, efavirenz, etravirine, modafinil, nafcillin, genistein, ritonavir, thioridazine, tipranavir, semagacestat, talviraline, lopinavir, lersivirine,

Weak inducers:

amprenavir, aprepitant, armodafinil bexarotene, clobazam, danshen5, dexamethasone, echinacea, ginkgo (ginkgo biloba), glycyrrhizin, methylprednisolone, nevirapine, oxcarbazepine, pioglitazone, prednisone, pleconaril, primidone, raltegravir, rufinamide, sorafenib, telaprevir, terbinafine, topiramate, troglitazone, vinblastine, eslicarbazepine, ginseng, vemurafenib, boceprevir, sulfapyrazone, ticagrelor, vicriviroc/ritonavir, ritonavir, ticlopidine, brivacetam, stribild (combo of elvitegravir, cobicistat, emtricitabine, and tenofovir), quercetin. honey.yin zhi huang

Inhibitors

Strong inhibitors:

VIEKIRA PAK, indinavir/ritonavir, tipranavir/ritonavir, ritonavir, cobicistat (GS-9350), indinavir, ketoconazole, troleandomycin, telaprevir, danoprevir/ritonavir, elvitegravir/ritonavir, saquinavir/ritonavir, lopinavir/ritonavir, itraconazole, voriconazole, mibefradil, LCL161, clarithromycin, posaconazole, telithromycin, grapefruit juice, conivaptan, nefazodone, nelfinavir, saquinavir, idelalisib, boceprevir, darunavir/ritonavir

Moderate inhibitors:

Erythromycin, fluconazole, darunavir, diltiazem, dronedarone, crizotinib, atazanavir, aprepitant, casopitant, amprenavir, faldaprevir, imatinib, verapamil, netupitant, nilotinib, tofisopam, cyclosporine, ACT-178882, ciprofloxacin, schisandra, sphenanthera, isavuconazole, cimetidine, FK1706 Ferula asafetida resin (Ferula assa-foetida)

Weak inhibitors:

Tabimorelin, ranolazine, amlodipine, lomitapide, fosaprepitant (IV), Seville orange juice, amiodarone, chlorzoxazone, M100240, fluvoxamine, ranitidine, fostamatinib, goldenseal, clotrimazole, tacrolimus, palbociclib, cilostazol, ticagrelor, peppermint oil, ivacaftor, GSK2248761, Guan Mai Ning, AZD2327, resveratrol, roxithromycin, suvorexant, propiverine, isoniazid, berberine, oral contraceptives, delavirdine, daclatasvir, simeprevir, atorvastatin, tolvaptan, almorexant, GSK1292263, evacetrapid, linagliptin, lacidipine, cranberry juice, pazopanib, everolimus, blueberry juice, AMD070, alprazolam, Tong Xin Luo, bicalutamide, sitaxentan, azithromycin, ginkgo, teriflunomide, Garden Cress seeds (Lepidium sativum)

Reference: Internal Clinical Pharmacology Drug-drug interaction (DDI) memo, updated May2016 which summarizes DDI data from three sources including the FDA's "Guidance for Industry, Drug Interaction Studies", the University of Washington's Drug Interaction Database, and Indiana University School of Medicine's Drug Interaction Table.

Table 6-6 Pgp substrates, inducers, inhibitors

Category

NTI substrates of P-gp¹:

digoxin, quinidine, paclitaxel, cyclosporine, sirolimus, tacrolimus, fentanyl, phenytoin

Substrates of Pgp (≥2X AUC change)²

aliskiren, ambrisentan, atorvastatin, atorvastatin acid, azithromycin, cerivastatin, colchicine, CP-481,715, cyclosporine, dabigatran, digoxin, docetaxel, domperidone, doxorubicin, fentanyl, fexofenadine, lapatinib, linezolid, loperamide, maraviroc, nevirapine, paclitaxel, proguanil, quinidine, ranolazine, ritonavir, saquinavir, simvastatin, sirolimus, sofosbuvir, tacrolimus, ticagrelor, topotecan, voclosporin

Substrates of Pgp mentioned in US label³

afatinib, alfuzosin, aliskiren, alogliptin, ambrisentan, apixaban, apremilast, Aprepitant, boceprevir, bosentan, carvedilol, carvedilol, caspofungin, ceritinib, citalopram, colchicine, cyclosporine, dabigatran, digoxin, doxepin, doxorubicin, eribulin, everolimus, fidaxomicin, fluvastatin, fosamprenavir, gatifloxacin, idelalisib, iloperidone, indacaterol, irbesartan, lacosamide, lapatinib, levetiracetam, levofloxacin, linagliptin, losartan, maraviroc, mirabegron, moxifloxacin, naloxegol, nateglinide, nintedanib, olodaterol, pantoprazole, paroxetine, pazopanib, posaconazole, pravastatin, quinine, ranolazine, riociguat, risperidone, rivaroxaban, saquinavir, silodosin, simeprevir, sirolimus, sitagliptin, sorafenib, telaprevir, tenofovir, ticagrelor, tipranavir, tolvaptan, topotecan, umeclidinium, valsartan, vardenafil, vincristine, voriconazole

P-gp Inhibitors

alogliptin, amiodarone⁴, azithromycin, canaglifozin, captopril, carvedilol, clarithromycin, clopidrogel, conivaptan, cremophor RH0, curcumin, diltiazem, dronedarone, elacridar, eliglustat, erythromycin, felodipine, fluvoxamine, fostamatinib, ginko, indinavir, isavuconazole, itraconazole, ivacaftor, ketoconazole, lapatinib, lopinavir, mibefradil, milk thistle (silymarin, silibinin), mirabegron, nelfinavir, nifedipine, nitredipine, ombitasvir, paritaprevir, paroxetine, propafenone, quercetin, quinidine, quinine, ranolazine, rifampin, ritonavir, sequinavir, schisandra chinesis extract, simeprevir, St. John's wort extract (HYPERICUM PERFORATUM), survorexant, talinolol, telaprevir, telmisartan, ticagrelor, tipranavir, tolvaptan, valspodar, vandetanib, verapamil, voclosporin, vorapaxar.

P-gp Inducers

avasimibe, carbamazepine, danshen (Salvia miltiorhiza), efavirenz, genistein², phenytoin, quercetin², rifampin, St. Johns wort extract, garlic extract

Reference: Internal Clinical Pharmacology Drug-drug interaction (DDI) memo, updated May2016 which summarizes DDI data from three sources including the FDA's "Guidance for Industry, Drug Interaction Studies", the University of Washington's Drug Interaction Database, and Indiana University School of Medicine's Drug Interaction Table.

1 These drugs have both a narrow therapeutic index and an in vivo DDI outcome ascribed at least in part ascribed to Pgp (inhibition or induction) that exceeds a 20% change in AUC.

2 These drugs have in vivo DDI outcomes (inhibition) which are $\geq 2x$ increase in AUC and are at least in part ascribed to Pgp.

3 The US labels for these drugs have specific language on in vivo Pgp substrate status.

4 Dual P-gp and CYP3A4 inhibitor

Vaccinations

Immunosuppressants may affect the response to vaccination and vaccination during treatment with everolimus may therefore be less effective. The use of live vaccines should be avoided during treatment with everolimus.

Examples of live vaccines are: intranasal influenza, measles, mumps, rubella, oral polio, BCG, yellow fever, varicella, and TY21a typhoid vaccines.

Other prohibited concomitant therapy

Patients may not take any other mTOR inhibitors or other investigational treatments while on study treatment.

